6.4. Subset Analyses

Subset analyses as needed were described in Sections 6.2.1.3, 6.2.3.1.1, and 6.3.4 for the corresponding endpoints.

6.5. Baseline and Other Summaries and Analyses

6.5.1. Baseline Summaries

The demographic and baseline characteristics (see Section 3.4) will be summarized descriptively for the treatment group for the ITT, mITT, myITT-IA, and myITT-IM populations.

6.5.2. Primary Underlying Disease

The primary underlying disease at baseline will be summarized descriptively for the treatment group for the ITT, mITT, myITT-IA, myITT-IA, and myITT-IM populations. The data will be coded using MedDRA. The number and percentage of participants will be summarized by diagnosis.

6.5.3. Study Conduct and Participant Disposition

Participant disposition will be summarized for ITT, mITT, myITT-IA, and myITT-IM populations including the number and percentage of participants enrolled, treated, completed the study, discontinued from the study intervention.

Additionally, number and percentage of participants who discontinued from the study will be summarized by the primary reasons of discontinuation for ITT, mITT, myITT-IA, and myITT-IM population.

6.5.4. Study Treatment Exposure

Study treatment exposure will be descriptively summarized for treatment group for the Safety population. Extent of exposure is defined as the number of days between the start and the end date of study treatment, where the duration will be calculated by: (end date – start date + 1).

The total duration in days, duration of IV dosing only, and duration of oral dosing only will be summarized descriptively with n, mean, SD, median, minimum and maximum. The number and percent of participants with an extent of exposure will be summarized within the following day ranges: > 0 to ≤ 2 days, > 2 to ≤ 7 days, > 7 to ≤ 14 days, > 14 to ≤ 21 days, > 21 to ≤ 42 days, > 42 to ≤ 56 days, > 56 to ≤ 84 days, and > 84 days. In addition, cumulative exposure will be summarized by the number and percent of participants for the following categories: ≥ 1 day, ≥ 7 days, ≥ 14 days, ≥ 21 days, ≥ 28 days, ≥ 42 days, ≥ 56 days and ≥ 84 days.

6.5.5. Anti-infective and Medical History

Anti-infective history of all fungal (excluding IFD under study), viral, and bacterial infections within 4 weeks prior to first dose of study intervention and medical history will be summarized for ITT, mITT, myITT-IA, and myITT-IM. The data will be coded using MedDRA. The number and percentage of participants in each SOC/PT will be presented by alphabetic order.

6.5.6. Prior and Concomitant Medications

Prior medications are defined as any medications taken before study intervention started. The number and percentage of participants who took at least one prior medication as well as for each medication will be summarized. The number and percentage of participants with prior anti-fungal medication will be summarized separately.

Concomitant medications are defined as any medications that participants took after the first dose of study intervention and through 28 days after the last day of study intervention. The number and percentage of participants who took at least one concomitant medication as well as for each medication will be summarized. The number and percentage of participants with concomitant anti-fungal medication will be summarized separately.

CCI

Participants taking the same concomitant (or prior) medication multiple times will be counted once per that concomitant (or prior) medication. The summaries will be performed for ITT, mITT, myITT-IA, and myITT-IM populations.

6.5.7. Non-medication Procedure

Non-medication procedures will be coded using MedDRA.

Prior procedures are defined as procedures that participants started using prior to first administration of study intervention. Concomitant procedures are defined as any medications that participants took after the first dose of study intervention and through 28 days after the last day of study intervention.

The number and percentage of participants receiving non-medication procedures will be summarized by SOC/PT for ITT, mITT, myITT-IA, and myITT-IM populations. This summary will be done for prior and concomitant procedures separately.

6.5.8. Baseline IFD Characteristics

The assessment of IFD at baseline will be summarized as described in the following subsections. The summaries will be performed for mITT, myITT-IA, and myITT-IM populations. Baseline IFD characteristics is defined as the test obtained prior to the first dose and up to 7 days after the first administration of study medication.

6.5.8.1. Mycological Assessments

Mycological assessments at baseline will be summarized by number and percentage of participants in the following categories:

- Histopathology /Culture evidence of IFD
- Single serum or plasma: ≥ 0.7 to < 1.0 and bronchoalveolar lavage (BAL) GM ≥ 0.8
- Single serum or plasma: ≥ 1.0
- BAL GM: ≥ 1.0
- Two consecutive values of either serum, plasma or BAL fluid between ≥ 0.5 to < 1.0 (from two separate specimens of the same category)
- No mycological evidence available.

6.5.8.2. Pathogen(s) Causing IFD

Number and percentage of participants for each category of pathogen causing IFD will be summarized for the following categories (some of the categories may be updated based on data available):

- Aspergillus Species or Other Filamentous Fungi
- Mucorales Species Only
- Mould Species, Not Otherwise Specified

- Aspergillus Species Plus Other Mould Species
- No Pathogen Identified.

6.5.8.3. Location(s) of IFD

The following IFD location will be summarized by number and percentage of participants:

- LRTD only
- LRTD plus Other Organ
- Non LRTD only.

For participants with non-LRTD locations assessed, the following types of locations will be further summarized: BODY, Brain, Eye, LIVER, Sinus, Skinand Other.

6.5.8.4. Categorization of IFD

The following categories of IFD will be summarized with number and percentage of participants:

- Proven IM
- Proven IA
- Probable IM
- Probable IA
- Possible
- No IFD.

6.5.8.5. Clinical Signs and Symptoms

Clinical signs and symptoms will be summarized by number and percentage of participants in descending order. Baseline is defined as the signs and symptoms collected at Day 1 or Screening (if Day 1 data is missing). The summary will additionally based on ITT population in addition to mITT, myITT-IA, and myITT-IM populations. In addition, mycological assessments, pathogen(s) causing the IFD, location(s) of IFD, and categorization of IFD, signs and symptoms will be listed.

6.6. Safety Summaries and Analyses

- Analysis set: Safety population (Section 4).
- Analysis methodology: Different analysis methods will be performed for the safety variables as follows, respectively.

6.6.1. Adverse Events

All causality TEAEs and treatment-related TEAEs will be coded using MedDRA and will be presented as following:

- TEAEs overview (all causality TEAEs and treatment-related TEAEs)
- TEAEs by SOC and PT (all causality TEAEs and treatment-related TEAEs)
- Incidence and severity of TEAEs by SOC and PT (all causality TEAEs and treatment-related TEAEs)
- Treatment-Emergent SAEs by SOC and PT (all causality TEAEs and treatment-related TEAEs)
- Summary of TEAE Leading to Discontinuation of Study Drug (all causality TEAEs and treatment-related TEAEs)
- Summary of TEAE Leading to Deaths (all causality TEAEs and treatment-related TEAEs)
- Listing of SAE and deaths

6.6.2. Laboratory Data

All clinical laboratory values including Hematology, Chemistry and Urinalysis from a local laboratory will be summarized. Laboratory values (actual values and change from baseline) will be descriptively summarized by visit. The change from baseline for urinalysis will include pH parameter. Number and percentage of participants with shifts from baseline to post-baseline will be summarized for the following:

- 1) An upward shift from baseline to post-baseline (i.e. L to N, L to H, or N to H)
- 2) No change from baseline to post-baseline (i.e. L to L, N to N, or H to H)
- 3) A downward shift from baseline to post-baseline (i.e. H to N, H to L, or N to L).

The individual listing of laboratory data will also be generated with flagging of values outside the normal reference ranges

In addition, potential hepatotoxicity and nephrotoxicity will be summarize.

Assessment of Hepatotoxicity

Potential hepatotoxicity will be summarized descriptively. The number and percentage of participants who meet the following criteria based on either local or central laboratories

including post-baseline data collected within post-dosing window will be summarized for the following criteria.

- Alanine aminotransferase (ALT) or Aspartate aminotransferase (AST) > 3xULN, > 5xULN, > 10xULN, >20xULN
- ALT > 3xULN, > 5xULN, > 10xULN, >20xULN
- AST > 3xULN, > 5xULN, > 10xULN, >20xULN
- Alkaline phosphatase (ALP) > 1.5xULN, >3xULN
- Total Bilirubin >2xULN
- ALT or AST > 3xULN and Total Bilirubin > 1.5xULN
- ALT or AST > 3xULN and Total Bilirubin > 2xULN
- ALT or AST > 3xULN and ALP < 2xULN and Total Bilirubin > 2xULN

A participant may be counted more than once as the categories are not mutually exclusive (ie., a participant with a value >10xULN will be counted in both 3xULN and 5xULN categories). The analysis will be conducted by taking all post-baseline values.

Assessment of Nephrotoxicity

Serum creatinine either from local or central lab will be further analyzed by the following 3 categories:

- $\geq 25\%$, $\geq 50\%$, $\geq 100\%$ increase from baseline.

The categories are not mutually exclusive, thus a participant may be counted in more than one category. Participants with both baseline and at least one post-baseline will be included in this summary. The number and percentage of participants meeting the defined criteria will be summarized by treatment group in 2 ways: by taking all post-baseline values, and at EOT

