9.3.2. Safety Analyses

Safety variables will be summarized descriptively for the safety population. 95% CIs for the binary outcome of selected safety variables may be presented based on an exact binomial distribution.

The primary safety endpoint is the incidence rates of TEAEs by SOC and PT. A TEAE is defined as any AE that starts on or after the first administration of study intervention until 28 days after last dose of study intervention. Other key summaries of AEs include the summaries of

- TEAE related to study intervention
- Treatment-Emergent SAEs
- TEAE leading to discontinuation of study intervention
- TEAE leading to deaths
- All deaths

Vital signs will be listed and summarized by means and standard deviation (SD). Laboratory test values will be presented in change from baseline and shift tables and by individual listings with flagging of values outside the normal reference ranges. ECG findings will be presented by listings and frequency tables, as appropriate.

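### The planned laboratory shift summary pools return to normal with new abnormality, so it cannot count participants who became newly low or newly high

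*SAP*

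**What the plan says.** Protocol 9.3.2 commits to shift tables without giving their layout: "Laboratory test values will be presented in change from baseline and shift tables". SAP 6.6.2 supplies the layout. It announces "Number and percentage of participants with shifts from baseline to post-baseline will be summarized for the following" and then gives three rows, with L, N and H for low, normal and high:

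- "An upward shift from baseline to post-baseline (i.e. L to N, L to H, or N to H"
- "No change from baseline to post-baseline (i.e. L to L, N to N, or H to H"
- "A downward shift from baseline to post-baseline (i.e. H to N, H to L, or N to L"

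The same section plans by-visit descriptive statistics, counts above multiples of ULN for ALT, AST, ALP and bilirubin, and counts by percent rise in creatinine. It also plans a participant-level listing: "The individual listing of laboratory data will also be generated with flagging of values outside the normal reference ranges". Clinical laboratory variables are a secondary safety endpoint (Protocol 3, SAP 3.2), and the study's primary objective is safety.

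**The concern.** A shift table is useful because each participant's starting category is kept beside the later one. Collapsing it by direction discards that information. The upward row adds recovery from low (L→N) to new high values (N→H, L→H). The downward row adds recovery from high (H→N) to new low values (N→L, H→L). The unchanged row adds participants who stayed normal to those who stayed abnormal.

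This matters most for analytes that can be abnormal in both directions and may be abnormal at entry. Neutropenia, hematologic malignancy and liver disease are host factors in Protocol 10.9. Protocol 5.2 gives neutropenia that is not expected to resolve as an example of an excluding condition, so L→N is an expected course for neutrophils in those who enter neutropenic. There is no control group to show how much movement is recovery. The participant's own baseline category is therefore the main guide, and the summary pools across it.

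**Working it through.** **Inputs.** The number treated is 66 (Protocol 9.5). The only figure stated there is the chance of seeing at least one AE of 3% incidence: 1 − 0.97^66 = 0.866, which matches the plan's 86.6%. The point does not depend on it; only N = 66 is used below.

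**Step 1: what the rows determine.** Write each cell as baseline→post-baseline.

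- Upward U = LN + LH + NH, and newly high = LH + NH. Given U, newly high can be anything from 0 to U.
- Downward D = HN + HL + NL, and newly low = HL + NL. Given D, newly low can be anything from 0 to D.
- Newly low or high together therefore lies between 0 and U + D. The three rows narrow it no further.

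**Step 2: two tables with the same output.** All cell counts are assumed.

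| Cell | Table A | Table B |
|---|---|---|
| L→N | 20 | 0 |
| N→H | 0 | 20 |
| H→N | 10 | 0 |
| N→L | 0 | 10 |
| L→L | 18 | 18 |
| N→N | 16 | 16 |
| H→H | 2 | 2 |
| L→H, H→L | 0 | 0 |
| Total | 66 | 66 |

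The SAP summary is the same for both: upward 20/66 (30.3%), no change 36/66 (54.5%), downward 10/66 (15.2%). What a safety reader needs is very different:

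| Quantity | Table A | Table B |
|---|---|---|
| Returned to normal | 30 | 0 |
| Newly abnormal | 0 | 30 (30/66 = 45.5%) |
| Newly high / not high at baseline | 0/54 | 20/64 (31.3%) |
| Newly low / not low at baseline | 0/28 | 10/48 (20.8%) |

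Denominators: A has 38 low, 16 normal and 12 high at baseline, so 66 − 12 = 54 and 66 − 38 = 28. B has 18, 46 and 2, so 66 − 2 = 64 and 66 − 18 = 48.

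**Step 3: a single-analyte illustration, also assumed.** Suppose 30 of 66 start with low platelets, 20 of them recover, 2 others go N→H and none go L→H. The upward row reads 22/66 = 33%, and 20/22 = 91% of it is recovery.

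**Step 4: whether another planned output gives the count.**

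| Output | Counts participants? | Covers hematology and electrolytes? |
|---|---|---|
| By-visit values and changes (SAP 6.6.2) | No; recoveries and new abnormalities can offset each other in a mean | Yes |
| Liver thresholds (SAP 6.6.2) | Yes, but not by baseline category | No |
| Creatinine rise (SAP 6.6.2) | Yes, against own baseline | No |
| TEAE tables (SAP 6.1, 6.6.1) | Yes | Only abnormalities that qualify as AEs |
| Flagged listing (SAP 6.6.2) | No; requires counting by hand | Yes |

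None is a pre-specified count of new out-of-range values for neutrophils, platelets, hemoglobin, sodium or potassium, all of which are required tests in Protocol 10.2.

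**The case against.** Much of the case on the other side stands.

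- **Important abnormalities are captured elsewhere.** Protocol 8.3.4 and 10.3.1 and SAP 3.5.1 make clinically significant abnormalities AEs, including those that need intervention or interrupt treatment. They are then counted by SOC and PT in the primary safety table. This narrows the gap but does not close it. Findings attributed to the underlying disease are left out unless worse than expected, and other range crossings are not covered.
- **The named laboratory risk has its own analysis.** Liver enzyme changes are listed as a risk in the synopsis, and SAP 6.6.2 counts them at several thresholds. A reader might infer from the shift rows that the study cannot show laboratory harm at all. The documents do not support that.
- **The data are kept.** The listing allows a hand count for about 66 participants, and no test or decision rule depends on this table. A hand count is not, however, a pre-specified summary.
- **The time point is largely settled.** A reader might infer that the post-baseline value is undefined. The preceding sentence on laboratory values says by visit, and SAP Appendix 3 sets windows and selection rules. A by-visit shift is the natural reading, and a participant who is up at one visit and down at another is then no defect.
- **The protocol fixes no layout.** A reader might infer that the SAP breaks the protocol's promise of shift tables; it does not. Nor can the SAP be read as already providing the nine cells: it asks for number and percentage in three pooled categories.

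**Conclusion.** The point holds in limited form. The three-row summary cannot show how many participants became newly low or newly high on any analyte. For hematology and electrolytes no other planned summary supplies that count. In the worked example, the same output is compatible with 0 to 30 newly abnormal participants of 66. That range follows from the row definitions; the row totals of 20, 36 and 10 are assumed, as are the counts behind the 33% and 91%.

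A reader might infer that recovery from underlying disease will dominate the counts. The documents give no baseline abnormality rates, and neutropenia is one of many alternative host factors, so this is possible but not established. A reader might also infer that a full table would separate drug harm from recovery. It would separate new abnormality from recovery, but in a single-arm study it could not say whether a new low platelet count came from the drug, chemotherapy or disease.

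The primary endpoint and the mortality analyses are unaffected. This is a weakness in a secondary safety summary and is worth correcting before the tables are programmed.

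**What to change.** In SAP 6.6.2, replace the three pooled rows with the full table of baseline L/N/H by post-baseline L/N/H for each analyte, with a category for missing. Present it:

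1. by visit, using the Appendix 3 windows; and
2. for the lowest and, separately, the highest post-baseline value through 28 days after the last dose, the same limit as the TEAE definition in SAP 3.1. The Appendix 3 rule keeps the value closest to the scheduled day, so a by-visit table alone can miss a transient extreme.

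Add two counts per analyte: participants newly low among those not low at baseline, and participants newly high among those not high at baseline. Keep the liver and creatinine summaries and the listing as they are. SAP 6.6.4 already counts worsening of the ECG interpretation, so the same idea is in use elsewhere in the plan.

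The cost is SAP wording and a standard table shell, with more pages of output. No new data or visits are needed. Protocol 9 lets the SAP modify the outlined methods and calls for an amendment only for major changes to the primary endpoint or its analysis, so no protocol amendment is needed.

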5.2. Exclusion Criteria

Participants are excluded from the study if any of the following criteria apply:

Medical Conditions:

1. Participants with either chronic aspergillosis, aspergilloma, or ABPA.

2. Advanced HIV infection with CD4 count < 200 or acquired immunodeficiency syndrome-defining condition.
3. Any known or suspected condition of the participant that may jeopardize adherence to the protocol requirements or impede the accurate measurement of efficacy, for example, neutropenia not expected to resolve, participants with fungal endocarditis, fungal osteomyelitis, fungal meningitis, or palliative therapy only for underlying condition.
4. Participants who are unlikely to survive 5 days or participants on mechanical ventilation.
5. Known history of allergy, hypersensitivity to, or any serious reaction to the azole class of antifungals or to any component of the study intervention.
6. Participants with severe hepatic impairment (Child-Pugh Class C) at the time of enrollment.
7. Other medical or psychiatric condition including recent (within the past year) or active suicidal ideation/behavior or laboratory abnormality that may increase the risk of study participation or, in the investigator's judgment, make the participant inappropriate for the study.

Prior/Concomitant Therapy:

8. Concomitant use of efavirenz, ritonavir, etravirine, rifampicin/rifampin, rifabutin, nafcillin, ketoconazole, or St. John's Wort in the 5 days prior to first administration of study intervention.
9. Participants who have been administered more than 4 cumulative days of itraconazole, voriconazole, or posaconazole, for any reason, within the 7 days prior to the first administration of study intervention.
 - 1) Participants with applicable host factors who develop new evidence of IFD while on prophylactic therapy, for at least 14 days, with either an AmB product or an echinocandin, will be eligible for enrollment.
 - 2) Prior use of fluconazole of any duration and for any reason will be eligible for enrollment.

Prior/Concurrent Clinical Study Experience:

10. Previous administration with an investigational product or vaccine within 30 days (or as determined by the local requirement) or 5 half-lives preceding the first dose of study intervention used in this study (whichever is longer).

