9.5. Sample Size Determination

Initially approximately 56 participants were planned to be enrolled (assigned to study intervention) and approximately 53 participants were expected to be treated. With 53 treated participants, for AEs that are as common as 3% or more, there would have been a probability of 80% to observe at least 1 participant experiencing such AEs. The China regulatory agency suggested to expand the sample size. The sample size is modified to enroll approximately 70 participants, among which approximately 66 participants are expected to be treated. With 66 treated participants, for AEs that are as common as 3% or more, there is a probability of 86.6% to observe at least 1 participant experiencing such AEs.

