10.5. Appendix 5: Liver Safety: Suggested Actions and Follow-Up Assessments

Potential Cases of Drug-Induced Liver Injury

Humans exposed to a drug who show no sign of liver injury (as determined by elevations in transaminases) are termed “tolerators,” while those who show transient liver injury but adapt are termed “adaptors.” In some participants, transaminase elevations are a harbinger of a more serious potential outcome. These participants fail to adapt and therefore are “susceptible” to progressive and serious liver injury, commonly referred to as DILI. Participants who experience a transaminase elevation above $3 \times \text{ULN}$ should be monitored more frequently to determine if they are “adaptors” or are “susceptible.”

In the majority of DILI cases, elevations in AST and/or ALT precede T bili elevations ($>2 \times \text{ULN}$) by several days or weeks. The increase in T bili typically occurs while AST/ALT is/are still elevated above $3 \times \text{ULN}$ (ie, AST/ALT and T bili values will be elevated within the same laboratory sample). In rare instances, by the time T bili elevations are detected, AST/ALT values might have decreased. This occurrence is still regarded as a potential DILI. Therefore, abnormal elevations in either AST OR ALT in addition to T bili that meet the criteria outlined below are considered potential DILI (assessed per Hy’s law criteria) cases and should always be considered important medical events, even before all other possible causes of liver injury have been excluded.

The threshold of laboratory abnormalities for a potential DILI case depends on the participant’s individual baseline values and underlying conditions. Participants who present with the following laboratory abnormalities should be evaluated further as potential DILI (Hy’s law) cases to definitively determine the etiology of the abnormal laboratory values:

- Participants with AST/ALT and T bili baseline values within the normal range who subsequently present with AST OR ALT values $\geq 3 \times \text{ULN}$ AND a T bili value $\geq 2 \times \text{ULN}$ with no evidence of hemolysis and an alkaline phosphatase value $< 2 \times \text{ULN}$ or not available.
- For participants with baseline AST **OR** ALT **OR** T bili values above the ULN, the following threshold values are used in the definition mentioned above, as needed, depending on which values are above the ULN at baseline:

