 - Preexisting AST or ALT baseline values above the normal range: AST or ALT values ≥ 2 times the baseline values AND $\geq 3 \times \text{ULN}$; or $\geq 8 \times \text{ULN}$ (whichever is smaller).
 - Preexisting values of T bili above the normal range: T bili level increased from baseline value by an amount of $\geq 1 \times \text{ULN}$ **or** if the value reaches $\geq 3 \times \text{ULN}$ (whichever is smaller).

Rises in AST/ALT and T bili separated by more than a few weeks should be assessed individually based on clinical judgment; any case where uncertainty remains as to whether it represents a potential Hy’s law case should be reviewed with the sponsor.

The participant should return to the investigator site and be evaluated as soon as possible, preferably within 48 hours from awareness of the abnormal results. This evaluation should include laboratory tests, detailed history, and physical assessment.

In addition to repeating measurements of AST and ALT and T bili for suspected Hy's law cases, additional laboratory tests should include albumin, CK, direct and indirect bilirubin, GGT, PT/INR, total bile acids, and alkaline phosphatase. Consideration should also be given to drawing a separate tube of clotted blood and an anticoagulated tube of blood for further testing, as needed, for further contemporaneous analyses at the time of the recognized initial abnormalities to determine etiology. A detailed history, including relevant information, such as review of ethanol, acetaminophen/paracetamol (either by itself or as a coformulated product in prescription or over-the-counter medications), recreational drug, or supplement (herbal) use and consumption, family history, sexual history, travel history, history of contact with a jaundiced person, surgery, blood transfusion, history of liver or allergic disease, and potential occupational exposure to chemicals, should be collected. Further testing for acute hepatitis A, B, C, D, and E infection, liver imaging (eg, biliary tract), and collection of serum samples for acetaminophen/paracetamol drug and/or protein adduct levels may be warranted.

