PLUS	At least one clinical feature [b] as below
PLUS	At least one mycological criterion [c] as below

a. HOST FACTORS:

- Either recently resolved or ongoing neutropenia (neutropenia defined as absolute neutrophil count (ANC) $<0.5 \times 10^9/L$ [$< 500/mm^3$] for ≥ 10 days), temporally related to the onset of fungal disease

- hematologic malignancy
- receipt of an allogeneic hematopoietic stem cell transplant (HSCT) / bone marrow transplant (BMT)
- receipt of a solid organ transplant
- prolonged use of corticosteroids (excluding among patients with allergic bronchopulmonary aspergillosis) at a therapeutic dose of ≥ 0.3 mg/kg corticosteroids for ≥ 3 weeks in the past 60 days
- treatment with other recognized T-cell immunosuppressants (such as calcineurin inhibitors, tumor necrosis factors- α blockers, lymphocyte-specific monoclonal antibodies or immunosuppressive nucleoside analogs) during the past 90 days (participants whose underlying condition is rheumatologic in nature are not eligible for enrollment)
- treatment with recognized B-cell immunosuppressants, such as Bruton's tyrosine kinase inhibitors, eg, ibrutinib
- inherited severe immunodeficiency (eg, chronic granulomatous disease, STAT 3 deficiency, or severe combined immunodeficiency)
- acute graft-versus-host disease grade III or IV involving the gut, lungs, or liver that is refractory to first-line treatment with steroids
- chronic respiratory airway abnormality (chronic obstructive lung disease, bronchiectasis)
- Severe influenza (or other severe viral pneumonia, such as coronavirus disease 2019 [COVID-19]), liver disease, malnutrition, severe burns, diabetes

b. CLINICAL FEATURES:

Lower Respiratory Tract Disease (LRTD)

See [Table 8](#) below for a summary of status of invasive fungal disease at baseline for participants with LRTD.

The medical history must be established to exclude alternative etiologies and to distinguish between an acute or subacute presentation rather than a chronic pulmonary infection. Onset of clinical symptoms and/or physical findings within approximately 2 weeks prior to the first administration of study medication defines an acute or subacute pulmonary infection.

Either the presence of at least one of the following signs on computed tomography (CT) scan or high resolution computed tomography (HRCT) or magnetic resonance imaging (MRI):

For pulmonary aspergillosis:

- Dense, well-circumscribed lesion(s) with or without a halo sign

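### The hepatotoxicity threshold table in SAP 6.6.2 has no baseline condition, so raised liver tests that persist from entry are counted with new ones

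*SAP*

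**What the plan says.** SAP 6.6.2, under Assessment of Hepatotoxicity, lists cumulative rows: ALT and/or AST above 3, 5, 10 and 20xULN, ALP above 1.5 and 3xULN, total bilirubin above 2xULN, and three combinations. The most specific is "ALT or AST > 3xULN and ALP < 2xULN and Total Bilirubin > 2xULN". On which data count, it says "The analysis will be conducted by taking all post-baseline values". The creatinine table just below it is defined by percentage rise from baseline, and the QTcF table in SAP 6.6.4 has change-from-baseline rows as well as absolute ones. The liver table has neither.

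On who can enter, Protocol 5.2 excludes "Participants with severe hepatic impairment (Child-Pugh Class C) at the time of enrollment". It sets no numerical limit for transaminases or bilirubin. Exclusion 7 allows exclusion for a laboratory abnormality, by investigator judgment. Protocol 4.3 and 6.6 provide for participants with mild or moderate hepatic impairment, and the host factors in Appendix 9 include "liver disease, malnutrition, severe burns, diabetes".

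Protocol Appendix 5 takes a different approach to potential drug-induced liver injury (DILI). Its threshold depends on "individual baseline values and underlying conditions", with a separate limb for "Preexisting AST or ALT baseline values above the normal range". There, AST or ALT must reach at least twice baseline and at least 3xULN, or at least 8xULN. Bilirubin raised at baseline must rise by at least 1xULN or reach at least 3xULN. Its normal-baseline limb also requires no evidence of hemolysis and accepts ALP below 2xULN or unavailable. SAP 2.1 records no modification of the protocol's analysis plan.

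**The concern.** A row headed potential hepatotoxicity will be read as a statement about the drug. In a controlled trial, abnormality present at entry would appear in both arms and roughly cancel. Here there is no second arm, and the eligibility criteria make raised liver tests at entry foreseeable. The protocol synopsis lists raised transaminases and hepatitis among the potential risks, and laboratory variables are a secondary safety endpoint. If the table mixes carried-over with new elevations, its percentages cannot be interpreted alone or compared sensibly with the rates the protocol cites from other studies. Nor can a reader reconcile the combined row with the cases investigators work up under Appendix 5.

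**Working it through.** **1. The plan's own figure.** The only numerical basis for the safety sample is in Protocol 9.5: "With 66 treated participants, for AEs that are as common as 3% or more, there is a probability of 86.6% to observe at least 1". The check is 1 − 0.97^66 = 0.8661, which agrees. For the earlier sample size of 53, 1 − 0.97^53 = 0.8010 against the stated 80%. The hepatotoxicity table has no figure of its own. I take N = 66 and the 3% rate from this section.

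**2. Carried-over counts with no drug effect.** Let b be the share with ALT or AST above 3xULN at baseline, and s the share of those still above it in at least one later sample. Neither is in the documents; both are assumptions. Expected count = 66 × b × s. Chance of at least one = 1 − (1 − b·s)^66.

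| b | s = 100% | chance of ≥1 | s = 50% | chance of ≥1 |
|---|---|---|---|---|
| 2% | 1.32 | 74% | 0.66 | 49% |
| 5% | 3.30 | 97% | 1.65 | 81% |
| 10% | 6.60 | 99.9% | 3.30 | 97% |
| 20% | 13.20 | >99.9% | 6.60 | 99.9% |

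**3. Effect on the reported rate.** Suppose 3% of participants below the threshold at baseline truly develop a new elevation, and all carried-over elevations persist. The table's rate is b + 0.03(1 − b).

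| b | counted of 66 | of which new | carried-over share |
|---|---|---|---|
| 2% | 3.3 (4.9%) | 1.9 | 40% |
| 5% | 5.2 (7.9%) | 1.9 | 64% |
| 10% | 8.4 (12.7%) | 1.8 | 79% |
| 20% | 14.8 (22.4%) | 1.6 | 89% |

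The underlying new-onset rate is 3% in every line.

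**4. Baselines near the threshold.** Assume later values are log-normal around an unchanged baseline B (in xULN), with within-person CV 30% and six samples. Then σ = √ln(1 + 0.3²) = 0.294, and the chance that at least one value exceeds 3xULN is 1 − Φ(ln(3/B)/σ)^6. This gives 0.41, 0.85, 0.98 and 1.00 for B = 2, 2.5, 3 and 3.5. For these baselines the Appendix 5 transaminase limit is 2B, and 1 − Φ(ln 2/σ)^6 is about 0.05 (about 0.20 at CV 40%). The model allows no recovery and no regression to the mean, so it is an upper illustration. It compares single-analyte limits, not the combined definitions.

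**5. The combined row beside Appendix 5.** Values are in xULN; ALP is 1 unless stated and there is no hemolysis.

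| ALT / bilirubin at baseline | later | SAP row | Appendix 5 |
|---|---|---|---|
| 4 / 2.5 | 4 / 2.5 | counted | not met |
| 2 / 0.8 | 3.5 / 2.5 | counted | not met (3.5 is below 2 × 2) |
| 0.8 / 1.5 | 4 / 2.2 | counted | not met (bilirubin rise 0.7) |
| 1.5 / 1.2 | 3.5 / 2.3 | counted | met |
| 1 / 1 | exactly 3 / 2 | not counted | met |
| 0.8 / 0.8 | 5 / 3, ALP missing | not stated | met |

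The two rules can disagree in either direction.

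**6. Whether another planned output fills the gap.** Change from baseline is summarized by visit with mean, SD, median, minimum and maximum (SAP 5.2.2 and 6.6.2). This would reveal one extreme rise but not how many participants rose. The shift table has only low, normal and high, so high to high is no change whatever the size. Listings hold the information but do not count it.

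**The case against.** The strongest reply is that this is one descriptive table among several. Change from baseline with its maximum is planned, listings flag out-of-range values, and 66 participants can be reviewed line by line. A reader might infer that no planned output could reveal a worsening from a raised baseline. The documents do not support that: a tenfold rise would show in the maximum change and in the listing. What stands is narrower: no planned summary counts such participants.

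A reader might also infer that the SAP contradicts the protocol's Hy's law definition. It does not. No SAP row carries that label, and Appendix 5 is a trigger for individual work-up. Cases meeting it on repeat testing, with no other cause found, are reported as SAEs, and SAP 6.6.1 tabulates treatment-emergent SAEs. Case-level safety reporting is not lost. Strict versus inclusive inequalities matter only at exact equality.

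It is also tempting to say that the SAP pairs any ALT with any bilirubin regardless of date, or drops participants with missing ALP. The SAP is silent on both; these need a sentence, not a correction.

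Finally, not every raised baseline is counted. The value must exceed the row's multiple after baseline, and exclusion 7 may keep some such participants out. The counts above rest on assumed prevalence and persistence and are not estimates for this trial.

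**Conclusion.** The point holds for the threshold table. It has no baseline condition, entry permits raised liver tests, and there is no control arm, so a persistent baseline elevation above a row's multiple is counted as potential hepatotoxicity without any drug effect. If 2% to 20% of 66 enter above 3xULN, this is about 1 to 13 participants with full persistence and about 0.7 to 7 with half. The mechanism follows from the text; the size depends wholly on those two assumptions. Separately, no row reproduces the Appendix 5 laboratory definition, although SAP 6.6.4 does summarize ECG findings against Protocol Appendix 7. This is a cheap improvement to a descriptive secondary safety display. It does not affect the primary endpoint.

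**What to change.** In SAP 6.6.2:

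- Add a table of baseline against worst post-baseline value for ALT, AST, ALP and total bilirubin, in the same ULN bands, so that participants already above a threshold at baseline are shown separately. Splitting the lowest band at the ULN would also identify the near-threshold participants of step 4.
- Keep the current all-values counts alongside. Restricting each existing row to participants below its threshold at baseline is less suitable, because it breaks the cumulative nesting: someone going from 4 to 12xULN would count above 5 and 10xULN but not above 3xULN.
- Add one row counting participants who meet the Appendix 5 laboratory criteria: baseline-adjusted limits, inclusive inequalities, and ALP below 2xULN or not available.
- Do not require ALT/AST and bilirubin from the same sample date. Appendix 5 keeps cases in which AST/ALT had fallen by the time bilirubin rose. List separately the cases that need clinical judgment on hemolysis or on rises more than a few weeks apart.
- State how the existing combined rows treat sample timing and missing ALP.

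The cost is SAP wording, one extra table and one derived row. Baseline laboratory values are already defined in SAP 3.5.2, so no new data are needed. The downside is sparse cells with about 66 participants, plus a short clinical review of the listed cases.
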